PTNS in combination with anticholinergic medications has been studied and outcomes compared [16,17,18,19]. In most of these studies, when PTNS plus placebo is compared to PTNS in combination with an anticholinergic medication, the combination therapy was found to be more effective than PTNS plus placebo or an anticholinergic medication alone (Table 1). In previous systematic reviews, when PTNS alone was compared to medications (anticholinergics) alone, no difference was found and each monotherapy was considered to be equally efficacious [20,21].

Table 1: Summary of studies looking at combination of PTNS with anticholinergic medications

Author	Comparison	N	Results
Vecchioli-Scaldazza et al., 2018 [16]	Solifenacin versus posterior tibial nerve stimulation (PTNS) versus combination therapy (PTNS+solifenacin)	27	OAB-SS (overactive bladder symptom score) solifenacin vs. PTNS p=0.0039 solifenacin vs. solifenacin+PTNS p<0.0001 PTNS vs. solifenacin+PTNS p=0.009 PGI-I (patient global impression of improvement) SS vs. PTNS p=0.0017 SS vs. SS+PTNS p<0.0001 PTNS vs. SS+PTNS p=0.0002
Sancaktar et al., 2010 [17]	Tolterodine alone vs. stroller afferent neuro-stimulation (SANS)+Tolterodine	38	UUI episodes (per week) before therapy after therapy p Tolterodine alone 22.8±2.4 12.3±0.8 <0.001 Tolterodine+SANS 22.4±2.8 6.4±0.5 <0.001 P >0.05 <0.001
Eftekhar et al., 2014 [18]	Tolterodine alone vs. PTNS+Tolterodine	30	Comparison of UUI symptom specific distress pre vs. post treatment PTNS+tolterodine vs. tolterodine (p=0.03)
Kizilyel et al., 2015 [19]	PTNS vs. Tolterodine vs. PTNS + Tolterodine	30	Reduction in # of UUI episodes most significant in PTNS+tolterodine PTNS plus placebo (p<0.01) Tolterodine (P<0.05) PTNS+Tolterodine (P<0.001)

Because the older population of women is a major focus of this study, it remains important to focus on less invasive treatments that are better tolerated by the geriatric

population as a whole. Therefore, because PTNS offers a less invasive approach to third line therapy and because mirabegron does not have the negative cognitive effects that anticholinergic meds cause in the geriatric population, this combination of PTNS + mirabegron offers great potential for providing better treatment for UUI/OAB, especially in women 70 years of age or greater.

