- Uncontrolled hypertension
- Hypersensitivity to mirabegron
- Superficial and/or deep skin infection where PTNS intervention is required
- Spinal cord injury or clinically significant neurological disorders known to affect urgency urinary incontinence
- Bleeding diathesis
- Failure of previous third line treatment options such as sacral neuromodulation, PTNS, or Botox
- Pacemaker, implantable defibrillator
- Current use of Interstim sacral nerve stimulator or TENS in the pelvic region, back, or legs
- Coagulopathy
- Chronic swollen, infected, inflamed skin or skin eruptions (e.g., phlebitis, thrombophlebitis, varicose veins) in the region where the PTNS needles or surface electrodes would be placed
- Metal implant in foot/toes near TENS electrode location
- Marked sensory deficit (numbness) of feet or ankles in the region where the PTNS needles or surface electrodes would be placed
- Currently pregnant or planning to become pregnant during the course of the study
- Unwilling to use acceptable form of contraceptive if the participant is of childbearing potential
- Unable or unwilling to complete the 3-day bladder diary
- Visual impairment prohibiting reading the paper diary
- Inability to provide informed consent, complete questionnaires independently, or to attend intervention sessions
- Unable to speak, read, or write in English

Intervention

Prior to beginning the treatment intervention, patients who are currently on medical therapy will stop medical therapy 2 weeks prior to the start of the trial. One arm of the study will receive PTNS combined with mirabegron and the other arm of the study will receive PTNS with placebo. In the PTNS with mirabegron arm, the patient will take a 50 mg dose daily for 12 weeks of the trial. In the PTNS with placebo arm, the patient will receive a placebo daily during the 12-week trial. PTNS will be performed as described: The percutaneous approach entails insertion of a 36-gauge needle electrode at a 60 degree angle approximately 5 cm or 3 finger breadths cephalad to the medial malleolus and posterior to the tibia. A portable electrical stimulator delivers an adjustable current in the range of 0.5-9 mA. The generators commonly are set for a pulse frequency of 20 Hz with a goal of creating a motor and/or sensory response in the foot. The stimulation sessions last for 30 min once per week for 12 continuous weeks.

Primary Outcome

Change in the number of UUI episodes over a 3-day voiding diary pre- vs. post-treatment.

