Randomization/Allocation

Patients will be randomized to the PTNS with mirabegron group or PTNS with placebo group in a 1:1 fashion using variable size permuted blocks of 2, 4, and 6. A sequentially numbered sealed envelope will be selected to reveal the randomized intervention. This will be done by a member of the research team on the day of the first PTNS treatment. Subjects will be blinded to which group they are assigned. Allocation concealment will be ensured by using a centralized service to provide sequentially numbered, opaque, sealed envelopes.

Sample Size Calculation

The main hypothesis is that the women in the PTNS with mirabegron group will have more improvement in the number of UUI episodes than women in the PTNS plus placebo group. Given this hypothesis, based on existing data,[17] a 2-sided alpha=0.05, the estimate for that difference in improvement has been estimated to be 2.5 UUI episodes over a 3-day bladder diary pre-vs. post-treatment with a standard deviation of 3 and a power of 0.80. Assuming an attrition rate of 10%, the total N per arm is estimated to be 27 subjects (a total of 54 subjects) for this study. The sample size estimation results are summarized in Table 2.

Table 2: Power analysis for change in UUI episodes pre-vs. post-treatment

Detectable Δ	Standard Deviation	Power	N
2.5	2	0.85	13
2.5	2	0.90	15
*2.5	3	0.80	24
2.5	3	0.85	27

Data analysis

[figure not shown]
For the primary analysis, an intention-to-treat analysis including all eligible patients randomizing to treatment will be used. Baseline clinical and demographic data will be compared between groups. The primary outcome (changes in the number of UUI episodes pre- vs. post-treatment) will be compared via general linear models.

Potential Pitfalls

The plan is to recruit 54 subjects based on the estimated sample size over a 12-18 month study period. Recruitment will be accomplished through multiple co-investigators in the division of

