We had 20 complete in the Active Arm and 26 complete in the Placebo Arm. You all have the data sheet. We have complete data for all initial visits. The 8 patients that we do not have End of Study Data for are the ones who fell out after randomization.

So, for statistical analysis, we have the Demographic Data as I have listed and we want comparisons between the two groups as one would do in an RCT. Secondly, the primary outcome is the change in the

number of UIs (urge urinary incontinence episodes) over a 3 day bladder diary pre-trial to the number of UIs post-trial on a 3 day bladder diary. Then compare them between the two groups.

Other components of the 3 day bladder diary include number of SUI (stress urinary incontinence) episodes changes pre vs. post, number of daytime voids pre vs. post, number of nighttime voids pre vs. post, and number of pads used pre vs. post.

Secondary outcomes also include the questionnaires of IIQ7, UDI 6, and OABQSF changes pre vs. post-trial and comparing them.

This should be laid out in the data table.

Thank you!

[name]

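### The primary model for change in UUI episodes names no baseline covariate, so as written it is an unadjusted change-score comparison that gives up precision the collected baseline diary could supply

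*Combined protocol and SAP*

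**What the plan says.** The Primary Outcome section defines the endpoint as "Change in the number of UUI episodes over a 3-day voiding diary pre- vs. post-treatment". The Data analysis section then states: "The primary outcome (changes in the number of UUI episodes pre- vs. post-treatment) will be compared via general linear models". The only use it gives to baseline data is a comparison between groups. The closing Statistical Analysis section repeats the endpoint as pre-to-post change in the 3-day count and continues: "Then compare them between the two groups". Neither section names a covariate.

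The Sample Size Calculation is on the change scale. It uses "a 2-sided alpha=0.05", and "the estimate for that difference in improvement has been estimated to be 2.5 UUI episodes over a 3-day bladder diary", "with a standard deviation of 3 and a power of 0.80". Table 2 gives 24 per arm for that row, and allowing for 10% attrition makes it 27. Randomization is 1:1 in permuted blocks, with no stratification by baseline UUI count stated.

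The baseline diary is collected after washout (Protocol in detail). The Statistical Analysis section reports 20 completers on active and 26 on placebo, and says of baseline: "We have complete data for all initial visits".

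**The concern.** A general linear model can carry covariates, but this one is not given any. With arm as the only term, it is a two-sample comparison of change scores.

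Subtracting baseline in full amounts to assuming that a woman with one more episode at baseline has, on average, one more episode after treatment. When the true slope is below 1, a change score over-corrects chance differences in baseline between the arms. The estimate stays unbiased under randomization but carries avoidable noise. Blocked allocation without stratification on the count does nothing to limit such differences.

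This matters in a trial of this size. The number of women with end-of-study data is slightly below the 24 per arm on which the stated 0.80 power rests, and the variable that could recover precision is already recorded for every woman. Leaving covariates unnamed also means that adjusted and unadjusted results would both be compatible with the plan, so the choice could be made after seeing them.

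**Working it through.** **Inputs.** Two-sided alpha 0.05, difference 2.5, change SD 3, power 0.80 and 24 per arm (Sample Size Calculation, Table 2); 20 and 26 completers (Statistical Analysis). The pre-post correlation *r* and the ratio *k* of post SD to baseline SD are not in the documents and are assumed below.

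**1. The plan's own figure.** Noncentral-t power for an unadjusted two-sample t-test, with SE = SD × √(1/n₁ + 1/n₂):
- 24 v 24: SE = 3 × √(2/24) = 0.866, power 0.807. The smallest n reaching 0.80 is 24, as stated, and 24/0.9 rounds up to 27.
- The other three rows of Table 2 (13, 15, 27) reproduce in the same way.

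The sample size therefore corresponds to the unadjusted change comparison.

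**2. Unadjusted analysis of the completers.** 20 v 26: SE = 3 × √(1/20 + 1/26) = 0.892. Power is 0.782, and the 95% CI half-width is 2.015 × 0.892 = 1.80 episodes.

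**3. Effect of adding baseline.** Let the baseline SD be *s*, the post SD *ks* and the correlation *r*, the same in both arms.
- Variance of change: s²(1 + k² − 2rk)
- Residual variance given baseline: s²k²(1 − r²)
- Difference between the two: s²(1 − rk)²

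The difference is never negative and is zero only when the slope *rk* equals 1. The ratio of adjusted to unadjusted variance is k²(1 − r²)/(1 + k² − 2rk), which at k = 1 is (1 + r)/2.

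**4. Results with equal SDs (k = 1), 20 v 26.** The change SD is held at 3. One degree of freedom is charged (43 df), and the variance is inflated by 43/42 for expected chance baseline imbalance.

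| Assumed r | Variance ratio | Power | 95% CI half-width |
|---|---|---|---|
| unadjusted | 1 | 0.78 | 1.80 |
| 0.3 | 0.65 | 0.92 | 1.47 |
| 0.5 | 0.75 | 0.88 | 1.58 |
| 0.7 | 0.85 | 0.84 | 1.68 |
| 0.9 | 0.95 | 0.79 | 1.77 |

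For example, at r = 0.5: SE = 0.892 × √0.75 × √(43/42) = 0.782, and 2.017 × 0.782 = 1.58. The net gain disappears at about r = 0.95. Simulation with bivariate normal data (20,000 runs per setting) gave adjusted power 0.920, 0.879, 0.833 and 0.794, unadjusted power 0.78 to 0.79, and type I error 0.050 to 0.051 for both.

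**5. Unequal SDs (k assumed), same four values of r.**
- k = 0.75: variance ratios 0.46, 0.52, 0.56, 0.50; power 0.98, 0.96, 0.95, 0.97.
- k = 1.25: variance ratios 0.78, 0.89, 0.98, 0.95; power 0.86, 0.82, 0.78, 0.79.
- Least favourable case, slope exactly 1 (for example k = 1.25, r = 0.8): power 0.772 against 0.782 unadjusted.

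**6. Evidence on direction.** Table 1 gives before and after spreads for the study on which the sample size is based. One arm reads "Tolterodine+SANS 22.4±2.8 6.4±0.5 <0.001"; the other went from 2.4 to 0.8. The ratios are 0.5/2.8 = 0.18 and 0.8/2.4 = 0.33, and they are the same whether the ± values are SDs or standard errors, provided n is unchanged. Because the slope is *rk* and r is at most 1, the slope in that study was at most 0.33.

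**The case against.** - **Unspecified is not the same as unadjusted.** The general linear model family includes the adjusted model, and a sample size computed without covariates is also compatible with a planned adjustment. This stands as far as it goes: the fault is an incomplete specification. But every readable description of the analysis is a bare comparison of change, and a plan that allows both versions does not fix the primary result. A figure under Data analysis is not reproduced in the text available, so its content could not be checked.
- **Dropout, not the model, produced the 0.78.** Correct. Eight of 54 women (15%) were lost against 10% planned, and even a 23 v 23 split would give 0.789. The shortfall is small and rests on planning values. It shows only that there is no power to spare.
- **The gain is not guaranteed.** Correct. It depends on *r* and *k*, and Table 1 concerns a different drug comparison with weekly counts, so it indicates direction only. The possible loss is about one power point; the possible gain on this grid is about 20.
- **The data are counts.** The power figures assume normality, and skew or a floor at zero would change them. The variance identity in step 3 does not require normality.
- **Randomization does not protect the completers.** Also correct. With 7 v 1 dropout, adjusted and unadjusted completer analyses could differ by more than precision if dropout is related to baseline count. Adjustment does not cure that.

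**Conclusion.** The concern holds. The primary analysis as written is an unadjusted change-score comparison, and a more precise estimate of the same mean difference is available from data already held. With equal pre and post SDs and assumed correlations of 0.3 to 0.7, the variance falls by 35% to 15%, power at 20 v 26 rises from 0.78 to between 0.92 and 0.84, and the CI half-width falls from 1.80 to between 1.47 and 1.68 episodes. At r = 0.9 the gain is about one power point.

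These sizes rest on the plan's difference of 2.5 and change SD of 3, and on assumed values of *r* and *k*. The stated sample size is not wrong, and under full follow-up the unadjusted estimate is not biased. The issue is precision and an open analytic choice.

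**What to change.** In the SAP, specify the primary model as a general linear model of change in the 3-day UUI count on arm plus baseline 3-day UUI count, reporting the adjusted mean difference with its 95% CI. Using the post-treatment count as the outcome gives the same arm coefficient, so the stated endpoint is kept. Treat the diary and questionnaire secondary outcomes the same way, each with its own baseline value. Report the unadjusted comparison of change as a sensitivity analysis.

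The Statistical Analysis section was written after completers were counted. Unless a dated earlier specification exists, the report should therefore state that the covariate was chosen after data collection.

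Set out the handling of the eight women without end-of-study data separately, so that it fits the intention-to-treat statement.

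The cost is one degree of freedom, a few lines of text and the disclosure. No new data are needed.

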We had 20 complete in the Active Arm and 26 complete in the Placebo Arm. You all have the data sheet. We have complete data for all initial visits. The 8 patients that we do not have End of Study Data for are the ones who fell out after randomization.

So, for statistical analysis, we have the Demographic Data as I have listed and we want comparisons between the two groups as one would do in an RCT. Secondly, the primary outcome is the change in the

number of UIs (urge urinary incontinence episodes) over a 3 day bladder diary pre-trial to the number of UIs post-trial on a 3 day bladder diary. Then compare them between the two groups.

Other components of the 3 day bladder diary include number of SUI (stress urinary incontinence) episodes changes pre vs. post, number of daytime voids pre vs. post, number of nighttime voids pre vs. post, and number of pads used pre vs. post.

Secondary outcomes also include the questionnaires of IIQ7, UDI 6, and OABQSF changes pre vs. post-trial and comparing them.

This should be laid out in the data table.

Thank you!

[name]
